### **2.2 Secondary Objectives**

- 1) To evaluate the long-term survival of patients.
- 2) To evaluate the quality of life of patients.

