### **2.3.2 Secondary endpoints**

- ORR, PFS, OS, CR, PR and DOR (according to RECIST v1.1)
- Safety and adverse events (according to NCI CTC AE v4.0)
- Quality of life assessment (FACT-H&N.V4 Quality of Life questionnaire)

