## Appendix V FACT-H&N (V4) Quality of Life Questionnaire

The following reflect the conditions of patients with diseases similar to yours. Think back to your past 7 days and tick the number that best matches your condition. There is no right or wrong answer, please answer all questions intuitively

Physical well-being (**PWB**) in the past 7 days:

GP1 I had low energy

0. Not at all    1. A little bit                  2. Somewhat                  3. Quite a bit                  4. Very much

GP2 I had nausea

0. Not at all    1. A little bit                  2. Somewhat                  3. Quite a bit                  4. Very much

GP3 It was difficult for me to meet the needs of my family because of my poor health

0. Not at all    1. A little bit                  2. Somewhat                  3. Quite a bit                  4. Very much

GP4 I had pain

0. Not at all    1. A little bit                  2. Somewhat                  3. Quite a bit                  4. Very much

GP5 I was affected by side effects of treatment

0. Not at all    1. A little bit                  2. Somewhat                  3. Quite a bit                  4. Very much

GP6 Generally, I felt like a patient

0. Not at all    1. A little bit                  2. Somewhat                  3. Quite a bit                  4. Very much

GP7 I had to be in bed

0. Not at all    1. A little bit                  2. Somewhat                  3. Quite a bit                  4. Very much

Social/Family well-being (**SWB**) in the past 7 days:

GS1 I felt close to my friends

0. Not at all    1. A little bit                  2. Somewhat                  3. Quite a bit                  4. Very much

GS2 I got emotional support from my family

0. Not at all    1. A little bit                  2. Somewhat                  3. Quite a bit                  4. Very much

GS3 I got support from my friends and neighbors

0. Not at all    1. A little bit                  2. Somewhat                  3. Quite a bit                  4. Very much

GS4 My family understood my illness

0. Not at all    1. A little bit                  2. Somewhat                  3. Quite a bit                  4. Very much

GS5 I was satisfied with family communication about my illness

0. Not at all    1. A little bit                  2. Somewhat                  3. Quite a bit                  4. Very much

If you have a partner or have sex, please answer items 13 and 14, otherwise, you can leave it blank.

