GS6 I felt close to my partner

0. Not at all    1. A little bit                  2. Somewhat                  3. Quite a bit                  4. Very much

GS7 I was satisfied with my sex life

0. Not at all    1. A little bit                  2. Somewhat                  3. Quite a bit                  4. Very much

Emotional well-being (**EWB**) in the past 7 days:

GE1 I felt sad

0. Not at all                                      1. A little bit                                      2. Somewhat                                      3. Quite a bit                                      4. Very much

GE2 I was satisfied with my ability to cope with the disease

0. Not at all                                      1. A little bit                                      2. Somewhat                                      3. Quite a bit                                      4. Very much

GE3 I am losing hope in the fight against my illness

0. Not at all                                      1. A little bit                                      2. Somewhat                                      3. Quite a bit                                      4. Very much

GE4 I felt nervous

0. Not at all                                      1. A little bit                                      2. Somewhat                                      3. Quite a bit                                      4. Very much

GE5 I was worried about dying

0. Not at all                                      1. A little bit                                      2. Somewhat                                      3. Quite a bit                                      4. Very much

GE6 I worried that my disease would get worse

0. Not at all                                      1. A little bit                                      2. Somewhat                                      3. Quite a bit                                      4. Very much

Functional well-being (**FWB**) in the past 7 days:

GF1 I was able to work (including housework)

0. Not at all                                      1. A little bit                                      2. Somewhat                                      3. Quite a bit                                      4. Very much

GF2 My work (including housework) was fulfilling

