0. Not at all                                      1. A little bit                                      2. Somewhat                                      3. Quite a bit                                      4. Very much

GF3 I was able to enjoy life

0. Not at all                                      1. A little bit                                      2. Somewhat                                      3. Quite a bit                                      4. Very much

GF4 I had accepted my illness

0. Not at all                                      1. A little bit                                      2. Somewhat                                      3. Quite a bit                                      4. Very much

GF5 I slept well

0. Not at all                                      1. A little bit                                      2. Somewhat                                      3. Quite a bit                                      4. Very much

GF6 I was enjoying the things I usually do for fun

0. Not at all                                      1. A little bit                                      2. Somewhat                                      3. Quite a bit                                      4. Very much

GF7 I was content with my quality of life right now

0. Not at all                                      1. A little bit                                      2. Somewhat                                      3. Quite a bit                                      4. Very much

Additional questions (**FACT-HN**) in the past 7 days:

hn1 I was able to eat the foods that I like

0. Not at all                                      1. A little bit                                      2. Somewhat                                      3. Quite a bit                                      4. Very much

hn2 My mouth was dry

0. Not at all                                      1. A little bit                                      2. Somewhat                                      3. Quite a bit                                      4. Very much

hn3 I had trouble breathing

0. Not at all                                      1. A little bit                                      2. Somewhat                                      3. Quite a bit                                      4. Very much

hn4 My voice had its usual quality and strength

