0. Not at all                                      1. A little bit                                      2. Somewhat                                      3. Quite a bit                                      4. Very much

hn5 I was able to eat as much food as I want

0. Not at all	1. A little bit	2. Somewhat	3. Quite a bit	4. Very much
hn6 I felt like my appearance (e.g., neck) had changed				
0. Not at all	1. A little bit	2. Somewhat	3. Quite a bit	4. Very much
hn7 I could swallow naturally and easily				
0. Not at all	1. A little bit	2. Somewhat	3. Quite a bit	4. Very much
hn8 I smoked				
0. Not at all	1. A little bit	2. Somewhat	3. Quite a bit	4. Very much
hn9 I drank alcohol (beer, wine or liquor)				
0. Not at all	1. A little bit	2. Somewhat	3. Quite a bit	4. Very much
hn10 I was able to communicate with others				
0. Not at all	1. A little bit	2. Somewhat	3. Quite a bit	4. Very much
hn11 I could eat solid foods				
0. Not at all	1. A little bit	2. Somewhat	3. Quite a bit	4. Very much

FACT-H&N Area of Scoring Method	Number of Entries	Score Range	Scoring Method
Physical well-being (PWB)	7	0–28	GP1+ GP2+ GP3+ GP4+ GP5+ GP6+ GP7
Social/Family well-being (SWB)	7	0–28	GS1+ GS2+ GS3+ GS4+ GS5+ GS6+ GS7
Emotional well-being (EWB)	6	0–24	GE1+ GE2+ GE3+ GE4+ GE5+ GE6
Functional well-being (FWB)	7	0–28	GF1+ GF2+ GF3+ GF4+ GF5+ GF6+ GF7
Functional Assessment of Cancer Therapy - General (FACT-G)	27	0–108	PWB+ SWB+ EWB+ FWB
Head and neck subscale (HNS)	9+2	0–36	hn1+hn2+hn3+hn4+hn5+hn6+hn7+hn10+hn11
Total score	38	0–144	PWB+ SWB+ EWB+ FWB+HNS

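### The Appendix V scoring table sums 15 problem-worded items without reversing them, so physical well-being is inverted and the emotional, head-and-neck, FACT-G and total scores mix opposite directions

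*Protocol*

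**What the plan says.** Protocol section 2.2 lists two secondary objectives, one of which is "To evaluate the quality of life of patients". Section 2.3.2 makes the FACT-H&N (version 4) questionnaire a secondary endpoint. Appendix V prints the items and ends with a table that has a column for the scoring method.

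- All items share one response scale, 0 (not at all) to 4 (very much).
- Some items describe problems, such as "GP2 I had nausea". Others describe good status, such as "GS1 I felt close to my friends" and "GF3 I was able to enjoy life".
- The emotional subscale holds both kinds. "GE2 I was satisfied with my ability to cope with the disease" stands beside items on sadness, loss of hope, nervousness and worry.
- Physical well-being (PWB) is scored as "GP1+ GP2+ GP3+ GP4+ GP5+ GP6+ GP7". The other subscales are plain sums of the same form, and the head-and-neck subscale (HNS) leaves out hn8 and hn9.
- The total is "PWB+ SWB+ EWB+ FWB+HNS".

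Neither the table nor any other part of the protocol says that an item is to be reversed, or which end of a score is favourable.

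**The concern.** A summed score has a meaning only if its items point the same way. Here a patient who reports more nausea and pain receives a higher score on a subscale named for physical well-being. That subscale is then added, with the same sign, to subscales on which higher means better.

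This is a complete, explicit formula, not an unstated detail, and anyone who programs the table as printed will get these scores. The trial has one arm, so no control group would show the anomaly. Two of the affected items, GP2 (nausea) and GP5 (side effects of treatment), bear directly on tolerability, and section 4.6.8 names nausea among the gastrointestinal events seen with the drug. At stake are the direction and size of a secondary result that a reader would take as a measure of well-being.

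**Working it through.** **Inputs**, all from Appendix V: the item wording, the 0–4 response scale and the scoring table.

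**Step 1. Reproduce the printed range.** Scored items: 7 + 7 + 6 + 7 + 9 = 36, and 36 × 4 = 144. FACT-G: 7 + 7 + 6 + 7 = 27, and 27 × 4 = 108. Both match the table.

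**Step 2. Class the scored items by wording.**

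- Problem items: GP1–GP7 (7); GE1 and GE3–GE6 (5); hn2, hn3 and hn6 (3). Sum: 15.
- Good-status items: GS1–GS7 (7); GE2 (1); GF1–GF7 (7); hn1, hn4, hn5, hn7, hn10 and hn11 (6). Sum: 21.
- Check: 15 + 21 = 36.

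**Step 3. Score the two extreme patients.** The best patient answers 4 to every good-status item and 0 to every problem item. The worst patient does the opposite. Under the printed sums, best = 4 × (good-status items) and worst = 4 × (problem items). With each problem item entered as 4 − response, best = 4 × (all items) and worst = 0.

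| Score | Problem items | Good-status items | Printed best / worst | Reversed best / worst |
|---|---|---|---|---|
| PWB | 7 | 0 | 0 / 28 | 28 / 0 |
| SWB (social/family) | 0 | 7 | 28 / 0 | 28 / 0 |
| EWB (emotional) | 5 | 1 | 4 / 20 | 24 / 0 |
| FWB (functional) | 0 | 7 | 28 / 0 | 28 / 0 |
| FACT-G | 12 | 15 | 60 / 48 | 108 / 0 |
| HNS | 3 | 6 | 24 / 12 | 36 / 0 |
| Total | 15 | 21 | 84 / 60 | 144 / 0 |

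The printed total therefore separates the best from the worst patient by 84 − 60 = 24 points, against 144 after reversal. The printed maximum of 144 goes to a patient who answers 4 to everything, symptoms included.

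**Step 4. Effect on change scores.** Let *P* be the summed rise on problem items and *G* the summed fall on good-status items when a patient worsens. The printed total changes by *P* − *G*. The reversed total changes by −*P* − *G*.

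- All seven PWB items worsen by one point and nothing else changes (*P* = 7, *G* = 0): printed +7, reversed −7.
- Every scored item worsens by one point (*P* = 15, *G* = 21): printed −6, reversed −36. The sign is right, but the change is 6/36 = one sixth of its proper size.

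**Step 5. Sensitivity to hn6.** This item says only that appearance has changed, so it is the least explicit of the 15. If it is treated as neutral with a fixed response *c*, there are 14 problem items. The printed best is 84 + *c* and the printed worst is 56 + *c*, a span of 28. The conclusion is unchanged.

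**The case against.** Several points on the other side stand.

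- *Not every score is wrong.* SWB and FWB, 14 of the 36 scored items, contain only good-status items and are correct as printed. PWB is uniformly inverted, loses no information and can be recovered by flipping it. A reader might infer that the whole table fails to measure quality of life. The item wording supports that for the scores that add opposite directions (EWB, HNS, FACT-G and the total), not for the others.
- *Toxicity does not always look like improvement.* A reader might infer that it does. By step 4, the printed total rises only when worsening on the problem items exceeds worsening on the good-status items. Under general deterioration it can still fall, but by too little.
- *The printed ranges are not evidence of error.* They hold for a plain sum with or without reversal.
- *Little else depends on the score.* The primary endpoint is the disease control rate (section 2.3.1). No decision rule or sample size uses FACT-H&N, section 9.3 does not name it, and adverse events are graded separately under section 7.

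One objection has less force. Scoring detail is often left to a statistical analysis plan, and one that is not at hand might reverse these items. The protocol, however, does not leave the matter open. It prints a specific formula, and a plan that reversed the items would contradict it.

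**Conclusion.** The concern holds in this limited form. The scoring rule as printed inverts PWB, mixes directions within EWB and HNS, and carries both faults into FACT-G and the total. The distance between the best and worst totals shrinks from 144 points to 24. Each one-point worsening on a problem item moves the total by 1 in the wrong direction, so symptom worsening is masked, or reversed in sign if other items are stable.

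The conclusion rests only on the item wording, the common response scale and the table. The single debatable classification, hn6, does not alter it. How far an observed mean change would be distorted depends on which items move, and the protocol gives no basis for putting a figure on that.

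The fault is confined to a secondary endpoint and can be corrected at analysis, provided item-level responses are kept. It should be fixed, but it does not threaten the primary conclusion.

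**What to change.** In the Appendix V scoring table, enter GP1–GP7, GE1, GE3, GE4, GE5, GE6, hn2, hn3 and hn6 as 4 minus the response before summing. State that a higher score is better for every subscale, for FACT-G and for the total. The item lists for SWB and FWB, and all printed ranges, stay as they are.

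The cost is one added rule in the appendix and the same rule wherever the scores are programmed. No new data are needed. Questionnaires already completed can be rescored if the individual item responses, and not only subscale totals, have been stored. The sponsor should confirm this, because the protocol does not say.
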